APPENDIX C. RECOMMENDED MSCT PROCEDURES

C.1 Introduction

Multi-slice Computed Tomography (Cardiac MSCT) is used to evaluate aortic valve anatomy, determine aortic root dimensions for device sizing, and to evaluate peripheral vessel dimensions and anatomy. The following sections are intended as recommended guidelines for acquiring the images for assessing anatomical suitability for implantation.

C.2 General Requirements

- Multi-detector CT scanner (64-slice minimum) with ECG-gating capability.
- ECG-gated contrast enhanced aortic root (slice thickness of ≤ 1.0 mm)
- Temporal resolution should be optimized to reduce motion artifact.
- Spatial resolution should be as high as possible (goal is smallest isotropic voxel size)

C.3 ECG-gated Contrast Enhanced Scan of Aortic Root

Retrospective ECG-gated scans are recommended, which allows for reconstruction in various phases of the cardiac cycle and optimal evaluation of anatomic dimensions and valve morphology. Recommended scan parameters are listed in Table 17.

Prospective ECG-gated sequential scans (step-and-shoot) and high-pitch spiral scans with ECG-gating (flash spiral) are also acceptable. The following parameters are important to the optimum scan:

- Detector collimation 0.4-0.625 mm.
- Slice thickness ≤ 1.0 mm.
- The recommended coverage area is from superior to the aortic arch to inferior to the cardiac apex. The minimum required coverage area is from 50 mm above the aortic annulus to 10 mm below the aortic annulus.
- The recommended slice overlap is 0.4 mm (will result in isotropic voxels with a 20 cm field of view).

C.4 Post-processing

- Retrospective ECG-gated scans
 - Verify heart rate ECG triggers are at consistent place in cardiac cycle, edit if necessary. Additional editing/removal of arrhythmias may be performed.
 - Reconstruct at multiple phases (10 increments of 10%), with ≤ 1.0 mm slice thickness. If the system has the capability, also reconstruct a “best systolic” and “best diastolic” phase.
- Prospective ECG-gated scans (including flash spiral)
 - Reconstruct with medium soft kernel and slice thickness ≤ 1.0 mm (slice overlap of 0.4 mm recommended)

Table 17. Recommended scan parameters

Parameter	Recommendation
IV injection with iodine contrast	80-100 (320mg/ml or higher), modify per patient as appropriate
Injection rate	4-6 mL/sec
Bolus tracking, delay	Delay time calculated using protocol for current scanner (bolus tracking or similar) with peak of contrast concentration in the ascending aorta during acquisition.
ECG-gating	Retrospective
Scan direction	Cranial-caudal
Scan coverage	From above the aortic arch to past the cardiac apex
Detector collimation	0.4 – 0.625 mm
Pitch	0.2–0.43 adapted to the heart rate
Dose modulation	Modulation and full current between 30 and 80% of the cardiac cycle
Slice thickness	0.8 mm
Slice overlap	0.4 mm
Reconstruction kernel	Medium Smooth
Post-processing	Retrospective ECG gating reconstruction algorithm that minimizes motion artifact. Reconstruct at multiple phases (10 minimum). Reconstructed slice thickness \leq 0.8 mm.

C.5 Required Aortic Root Measurements

The following measurements of the aortic root are obtained for assessing anatomical suitability:

- Aortic valve annulus perimeter (measured at systole if retrospective gating is used)
- Mean sinus of Valsalva diameter (measured at diastole)
- Mean sinus of Valsalva heights (measured at diastole)

C.6 Reformatting of Images⁴⁶

- Site image cross-hairs on aortic root in all windows where it is visible. Lock cross-hairs so they remain orthogonal for all steps.
- In the coronal window, rotate cross-hairs (horizontal line) counter-clockwise to align with virtual basal plane, (Figure 9, upper left panel).
- In the sagittal window, the horizontal line is rotated clockwise or counter-clockwise to align with virtual basal plane (Figure 9, lower left panel).
- On the newly defined double-oblique axial image, scroll up and down through the aortic root until the most caudal attachment points of the three native leaflets come into view (indicated by arrowheads in Figure 10). If one of the leaflets comes into view at a more cranial or caudal slice, adjust the coronal or sagittal cross-hairs until all three leaflets come into view on the same axial slice.

- For confirmation of the correct aortic annulus plane, scroll through the double oblique axial images starting in the mid sinus and ending at the level of the aortic annulus. The sinuses should appear to be relatively the same size at the level of the mid-sinus and the leaflets should all disappear equally at the level of the annulus.

[figure not shown]

Figure 9. Example images in original orientation (axial, coronal, and sagittal). Red curved arrow and line indicate adjustment of coronal and sagittal planes to align with aortic basal annulus.

[figure not shown]

Figure 10. Example images of reformatted oblique coronal (upper left), oblique sagittal (lower left), double oblique axial (upper right), and 3D reconstruction (lower right). Yellow arrowheads indicate most caudal attachment of three leaflets of the aortic valve.

C.7 Aortic Annulus Measurements

- Choose the cleanest systolic images for the aortic annulus measurements, either automatically (e.g., best systolic) or by manually identifying. Measurement on a diastolic image is also acceptable.
- Aortic annulus measurements should be completed on the properly reformatted double-oblique axial image at aortic annulus level, as described in Section C.6, Reformatting of Images.
- Trace the perimeter of the basal annulus (Figure 11, left). Place cross-hairs at site of basal annulus, create major diameter through the site, create minor diameter defined as perpendicular to major and through site (Figure 11, right).

[figure not shown]

Figure 11. Example of perimeter measurement (left) and major and minor diameter measurements (right).

C.8 Sinus of Valsalva Measurements

Choose the best diastolic images for measurement of sinus of Valsalva diameters and heights from images using the same reformatting technique as described in Section C.6, Reformatting of Images.

C.8.1 Sinus of Valsalva Diameters

- Select the double oblique axial image where the widest portion of the three sinuses is visible.
- Measure a diameter from each commissure through the site of the root to the opposite sinus. Complete for all three sinuses (Figure 12).

[figure not shown]

Figure 12. Example of sinus of Valsalva diameters

C.8.2 Sinus of Valsalva Heights

- The sinotubular junction is typically not co-planar with the aortic annulus. Therefore, a sinus of Valsalva height must be measured for each of the three sinuses. This height is defined as the distance between the aortic annular plane and the tallest point in the sinus.
- Choose the double oblique axial image so that it is located at the level of the aortic annulus. The reformatting line representing the double oblique axial image should now be visible in the oblique coronal and oblique sagittal images at the level of the aortic annulus.
- For the left coronary and non coronary heights, use the oblique coronal image. For the right coronary height, use the oblique sagittal image.
- To complete the measurement, scroll through the oblique coronal or sagittal image (depending on which sinus you are measuring) and locate the heights location of the sinotubular junction. On that image, measure the distance along the path of the aortic root from the aortic annular plane, marked by the reformatting line, to the sinotubular junction (Figure 13).

[figure not shown]

Figure 13. Examples of sinus of Valsalva heights; (A) left coronary; (B) non coronary; (C) right coronary

C.9 Anatomic Suitability and Valve Size Selection

Device Size	Aortic Annulus		Sinus of Valsalva	
	Perimeter (mm)	Mean Diameter (mm)	Mean Diameter (mm)	Mean Height (mm)
23 mm	56.5 – 62.8	18 – 20	≥ 25	≥ 15
26 mm	62.8 – 72.3	20 – 23	≥ 27	≥ 15
29 mm	72.3 – 81.6	23 – 26	≥ 29	≥ 15

APPENDIX D. DEFINITIONS: RISK SCORES AND OTHER CO-MORBIDITIES

D.1 Risk Scores

The Logistic EuroSCORE, EuroSCORE II and Society of Thoracic Surgeons' (STS) risk scores should be calculated at baseline for each subject using the online calculator:

- Logistic EuroSCORE: <http://euroscore.org/calcold.html>
- EuroSCORE II: <http://euroscore.org/calc.html>
- STS Risk Score: <http://riskcalc.sts.org/stswebriskcalc/#/>

The online calculators provide additional guidance and definitions for each of the parameters used to calculate the scores. For the Logistic EuroSCORE and EuroSCORE II, the definitions for each of the parameters can be found as notes under the online calculator. The variable definitions for the STS risk score model can be accessed by clicking on the field names in the online calculator.

D.2 Other Factors Not Captured by Traditional Risk Score³²

Co-morbidity	Definition/Criteria
Porcelain aorta or severely atherosclerotic aorta	Heavy circumferential calcification or severe atheromatous plaques of the entire ascending aorta extending to the arch such that aortic cross-clamping is not feasible.
Frailty	Slowness, weakness, exhaustion, wasting and malnutrition, poor endurance and inactivity, loss of independence Criteria: 
 • 5 meter walking time • Grip strength • BMI <20 kg/m² and/or weight loss 5 kg/yr • Serum albumin <3.5 g/dL • Cognitive impairment or dementia
Sever liver disease/cirrhosis	Any of the following: 
 • Child-Pugh class C • MELD score ≥10 • Portal-caval, spleno-renal, or transjugular intrahepatic portal shunt • Biopsy proven cirrhosis with portal hypertension or hepatocellular dysfunction
Hostile chest	Any of the following or other reasons that make redo operation through sternotomy or right anterior thoracotomy prohibitively hazardous: 
 • Abnormal chest wall anatomy due to severe kyphoscoliosis or other skeletal abnormalities (including thoracoplasty, Potts' disease) • Complications from prior surgery • Evidence of severe radiation damage (e.g. skin burns, bone destruction, muscle loss, lung fibrosis or esophageal stricture) • History of multiple recurrent pleural effusions causing internal adhesions
IMA or other critical conduit(s) crossing	A patent IMA graft that is adherent to the sternum such that injuring it during re-operation is likely. A patient may be considered extreme risk if any of the following

midline and/or adherent to posterior table of sternum	
are present:
 
 • The conduit(s) are radiographically indistinguishable from the posterior table of the sternum. • The conduit(s) are radiographically distinguishable from the posterior table of the sternum but lie within 2-3 mm of the posterior table.
Severe pulmonary hypertension Severe right ventricular dysfunction	
Primary or secondary pulmonary hypertension with PA systolic pressures greater than 2/3 of systemic pressure
 
Criteria as defined by the guidelines (e.g. TAPSE <15mm, RV end-systolic area >20 cm², etc)

APPENDIX E. DEFINITIONS: SAFETY ENDPOINTS AND EFFICACY EVENTS

Definitions of adverse events to be evaluated as clinical safety endpoints, other TAVI-related complications, and efficacy events are provided in Sections E.1, E.2, and E.3, respectively. Site investigators and the CEC will code events according to these definitions, using the associated code list provided in appendix G, Event Code List.

E.1 Safety Endpoint Definitions³²

Mortality	
Cardiovascular mortality	
Any of the following criteria:
 
 1) Death due to proximate cardiac cause (eg, myocardial infarction, cardiac tamponade, worsening heart failure) 2) Death caused by non-coronary vascular conditions such as neurological events, pulmonary embolism, ruptured aortic aneurysm, dissecting aneurysm, or other vascular disease 3) All procedure-related deaths, including those related to a complication of the procedure or treatment for a complication of the procedure 4) All valve-related deaths including structural or nonstructural valve dysfunction or other valve-related adverse events 5) Sudden or unwitnessed death 6) Death of unknown cause
Non-cardiovascular mortality	Any death in which the primary cause of death is clearly related to another condition (eg, trauma, cancer, suicide).

Myocardial Infarction	
Periprocedural MI (≤72 h after the index procedure)	
New ischemic symptoms (e.g, chest pain or shortness of breath), or new ischemic signs (e.g, ventricular arrhythmias, new or worsening heart failure, new ST-segment changes, hemodynamic instability, new pathological Q-waves in at least 2 contiguous leads, imaging evidence of new loss of viable myocardium or new wall motion abnormality) AND
 
Elevated cardiac biomarkers (preferable CK-MB) within 72 h after the index procedure, consisting of at least 1 sample post procedure with a peak value exceeding 15x as the upper reference limit for troponin or 5x for CK-MB. If cardiac biomarkers are increased at baseline (>99th percentile), a further increase in at least 50% post procedure is required AND the peak value must exceed the previously stated limit.

Spontaneous MI (>72 h after the index procedure)	
Any of the following criteria:
 
 1) Detection of rise and/or fall of cardiac biomarkers (preferably troponin) with at least 1 value above the 99th percentile URL, together with the evidence of myocardial ischemia with at least 1 of the following: 
 • Symptoms of ischemia • ECG changes indicative of new ischemia [new ST-T changes or new left bundle branch block (LBBB)] • New pathological Q-waves in at least 2 contiguous leads • Imaging evidence of a new loss of viable myocardium or new wall motion abnormality

	
2) Sudden, unexpected cardiac death, involving cardiac arrest, often with symptoms suggestive of myocardial ischemia, and accompanied by presumably new ST elevation, or new LBBB, and/or evidence of fresh thrombus by coronary angiography and/or at autopsy, but death occurring before blood samples could be obtained, or at a time before the appearance of cardiac biomarkers in the blood.
 
3) Pathological findings of an acute myocardial infarction

--	---

Stroke and TIA

Diagnostic criteria
 
1) Acute episode of a focal or global neurological deficit with at least 1 of the following:
 
 • change in the level of consciousness • hemiplegia, hemiparesis • numbness or sensory loss affecting 1 side of the body • dysphasia or aphasia • hemianopia • amaurosis fugax • other neurological signs or symptoms consistent with stroke 
Stroke: duration of a focal or global neurological deficit ≥ 24 h; OR < 24 h if available neuroimaging documents a new hemorrhage or infarct; OR the neurological deficit results in death
 
TIA: duration of a focal or global neurological deficit < 24 h, any variable neuroimaging does not demonstrate a new hemorrhage or infarct
 
2) No other readily identifiable non-stroke cause for the clinical presentation (e.g. brain tumor, trauma, infection, hypoglycemia, peripheral lesion, pharmacological influences), to be determined by or in conjunction with the designated neurologist
 
3) Confirmation of the diagnosis by at least 1 of the following:
 
 • Neurologist or neurosurgical specialist • Neuroimaging procedure (CT scan or brain MRI), but stroke may be diagnosed on clinical grounds alone

Stroke Definitions
 
Disabling stroke: an mRS score of 2 or more at 90 days and an increase in at least 1 mRS category from an individual's pre-stroke baseline
 
Non-disabling stroke: an mRS score of < 2 at 90 days or one that does not result in an increase in at least 1 mRS category from an individual's pre-stroke baseline

Stroke Classifications
 
Ischemic: an acute episode of focal cerebral, spinal, or retinal dysfunction caused by infarction of the central nervous system tissue
 
Hemorrhagic: an acute episode of focal or global cerebral or spinal dysfunction caused by intraparenchymal, intraventricular, or subarachnoid hemorrhage
 
Undetermined: insufficient information to allow categorization as ischemic or hemorrhagic

Bleeding Complications	
Life-threatening or disabling bleeding	
 1) Fatal bleeding (BARC type 5) OR 2) Bleeding in a critical organ, such as intracranial, intraspinal, intraocular, or pericardial necessitating pericardiocentesis, or intramuscular with compartment syndrome (BARC type 3b and 3c) OR 3) Bleeding causing hypovolemic shock or severe hypotension requiring vasopressors or surgery (BARC type 3b) OR 4) Overt source of bleeding with drop in hemoglobin ≥ 5 g/dL or whole blood or packed red blood cells (RBCs) transfusion ≥ 4 units* (BARC type 3b)
Major bleeding (BARC type 3a)	
 1) Overt bleeding either associated with a drop in the hemoglobin level of at least 3.0 g/dL or requiring transfusion of 2 or 3 units of whole blood/RBC, or causing hospitalization or permanent injury, or requiring surgery AND 2) Does not meet criteria of life-threatening or disabling bleeding
Minor bleeding (BARC type 2 or 3a, depending on the severity)	Any bleeding worthy of clinical mention (eg, access site hematoma) that does not qualify as life-threatening, disabling, or major
*Given one unit of packed RBC typically will raise hemoglobin concentration by 1 g/dL, an estimated decrease in haemoglobin will be calculated; BARC: Bleeding Academic Research Consortium ²⁹ ; RBC: red blood cell	

Note: With respect to blood transfusions, it is critical to acknowledge that a bleeding complication has to be the result of overt bleeding and cannot be adjudicated based on blood transfusions alone.

Acute Kidney Injury (up to 7 days post procedure)	
Stage 1	
 1) Increase in serum creatinine to 150%-199% (1.5-1.99 x increase compared with baseline) OR increase of ≥ 0.3 mg/dL (≥ 26.4 mmol/L) OR 2) Urine output < 0.5 mL/kg/h for > 6 but < 12 h
Stage 2	
 1) Increase in serum creatinine to 200%-299% (2.0%-2.99% increase compared with baseline) OR 2) Urine output < 0.5 mL/kg/h for > 12 but < 24 h
Stage 3	
 1) Increase in serum creatinine to $\geq 300\%$ (> 3 x increase compared with baseline) OR serum creatinine of ≥ 4.0 mg/dL (≥ 354 mmol/L) with an acute increase of at least 0.5 mg/dL (44 mmol/L) OR 2) Urine output < 0.3 ml/kg/h for ≥ 24 h OR 3) Anuria for ≥ 12 h

Vascular Access Site and Access Related Complications	
Major vascular complication	
 1) Any aortic dissection, aortic rupture, annulus rupture, left ventricle perforation, or new apical aneurysm/pseudoaneurysm OR 2) Access site or access-related vascular injury (dissection, stenosis, perforation, rupture, arterio-venous fistula, pseudoaneurysm, hematoma, irreversible nerve injury, compartment syndrome, percutaneous closure device failure) leading to death, life-threatening or major bleeding, visceral ischemia, or neurological impairment OR 3) Distal embolization (noncerebral) from a vascular source requiring surgery or resulting in amputation or irreversible end-organ damage OR 4) The use of unplanned endovascular or surgical intervention associated with death, major bleeding, visceral ischemia or neurological impairment OR 5) Any new ipsilateral lower extremity ischemia documented by patient symptoms, physical exam, and/or decreased or absent blood flow on lower extremity angiogram OR 6) Surgery for access site-related nerve injury OR 7) Permanent access site-related nerve injury
Minor vascular complication	
 1) Access site or access-related vascular injury (dissection, stenosis, perforation, rupture, arterio-venous fistula, pseudoaneurysms, hematomas, percutaneous closure device failure) not leading to death, life-threatening or major bleeding*, visceral ischemia, or neurological impairment OR 2) Distal embolization treated with embolectomy and/or thrombectomy and not resulting in amputation or irreversible end-organ damage OR 3) Any unplanned endovascular stenting or unplanned surgical intervention not meeting the criteria for a major vascular complication OR 4) Vascular repair or the need for vascular repair (via surgery, ultrasound-guided compression, transcatheter embolization, or stent-graft)
Percutaneous closure device failure	Failure of a closure device to achieve hemostasis at the arteriotomy site leading to alternative treatment (other than manual compression or adjunctive endovascular ballooning)

*Refer to VARC bleeding definitions

VALVE DYSFUNCTION REQUIRING REPEAT PROCEDURE
Any valve dysfunction that requires repeat procedure (e.g. balloon valvuloplasty, TAVI, or surgical AVR)

Note: Repeat procedures are reported on the appropriate e-CRF (Surgical Intervention or Catheter Reintervention)

E.2 Other TAVI Related Complications

Complication	Definition
Conversion to open surgery	Conversion to open sternotomy during the TAVI procedure secondary to any procedure-related complications
Unplanned use of cardiopulmonary bypass	Unplanned use of CPB for hemodynamic support at any time during the TAVI procedure
Coronary artery obstruction	Angiographic or echocardiographic evidence of a new, partial or complete, obstruction of a coronary ostium, either by the Evolut R prosthesis itself, the native leaflets, calcifications, or dissection, occurring during or after the TAVI procedure.
Ventricular septal perforation	Angiographic or echocardiographic evidence of a new septal perforation during or after the TAVI procedure
Mitral valve apparatus damage or dysfunction	Angiographic or echocardiographic evidence of new damage (chordae, papillary muscle, or leaflet) to the mitral valve apparatus or dysfunction (e.g. restrictions due to the Evolut R) of the mitral valve during or after the TAVI procedure
Cardiac tamponade	Evidence of new pericardial effusion associated with hemodynamic instability and clearly related to the TAVI procedure
Prosthetic valve thrombosis	Any thrombus attached to or near an implanted valve that occludes part of the blood flow path, interferes with valve function, or is sufficiently large to warrant treatment. *Valve-associated thrombus identified at autopsy in a patient whose cause of death was not valve related should not be reported as valve thrombosis.
Valve migration	After initial correct positioning, any observed movement (upward or downward) of the Evolut R within the aortic annulus from its initial position, with or without consequences.
Valve embolization	The Evolut R moves during or after deployment such that it loses contact within the aortic annulus
Ectopic valve deployment	Permanent deployment of the Evolut R in a location other than the aortic root
TAV in TAV deployment	Additional valve prosthesis is implanted within a previously implanted Evolut R because of sub-optimal device position and/or function, during or after the index procedure.
Hemolysis	Red cell destruction as evidenced by plasma free hemoglobin >50 mg/dl Minor hemolysis: No intervention required Major hemolysis: Requires intervention (e.g. iron supplements, transfusion, invasive intervention).
Frame fracture	Visual evidence on radiography or at explant of loss of contact between elements (cells) of the stent. Minor frame fracture: Does not require intervention, or is not associated with prosthetic valve dysfunction. Major frame fracture: Intervention required (e.g. reoperation, catheter re-intervention) or is associated with prosthetic valve dysfunction

PROSTHETIC VALVE ENDOCARDITIS

Any of the following:

1) Fulfillment of the following Duke criteria⁴⁷ for definite endocarditis:

- Histologic and/or microbiologic evidence of infection at surgery or autopsy, or
- 2 major criteria, or
- 1 major criteria or 3 minor criteria, or
- 5 minor criteria

Major and minor criteria are as follows:

Major Criteria:

- Blood cultures positive for Infective Endocarditis (IE)
 - Typical microorganisms consistent with IE isolated from two separate blood cultures, as noted below
 - Viridans streptococci, *Streptococcus bovis*, *Staphylococcus aureus*, or HACEK group
 - Community-acquired enterococci in the presence of a primary focus
 - Microorganisms consistent with IE isolated from persistently positive blood cultures defined as:
 - At least two positive cultures or blood samples obtained >12 hours apart, or
 - All of three, or a majority of four or more separate cultures of blood, the first and last sample obtained > one hour apart
 - Single blood culture positive for *Coxiella burnetii* or an antiphase I IG antibody titer >1:800
- **Evidence of endocardial involvement**
 - Positive results of echocardiography for IE defined as:
 - Oscillating intracardiac mass on a valve or supporting structures in the path of regurgitant jets or on implanted material in the absence of an anatomic explanation, or
 - Abscess, or
 - New partial dehiscence of a valvular prosthesis
 - New valvular regurgitation (worsening or changing or pre-existing murmur not sufficient)

Minor Criteria:

- **Predisposition:** predisposing heart condition or intravenous drug use
- **Fever:** temperature >38°C
- **Vascular phenomena:** major arterial emboli, septic pulmonary infarcts, mycotic aneurysm, intracranial hemorrhage, conjunctival hemorrhages, and Janeway's lesions
- **Immunological phenomena:** glomerulonephritis, Osler's nodes, Roth's spots, and rheumatoid factor
- **Microbiological evidence:** positive blood culture but does not meet a major criterion (as noted above) or serological evidence of active infection with organism consistent with infectious endocarditis.
- **Echocardiographic findings:** consistent with IE but do not meet a major criterion as noted above

If only 1 major and 1-2 minor criteria are fulfilled, or if only 3-4 minor criteria are fulfilled, the event will be coded as "possible endocarditis"

- 2) Evidence of abscess, paravalvular leak, pus, or vegetation confirmed as secondary to infection by histological or bacteriological studies during a re-operation
- 3) Findings of abscess, pus, or vegetation involving the Evolut R at autopsy

E.3 Efficacy Event Definitions³²

PROSTHETIC VALVE DYSFUNCTION	
Stenosis: mild	
For subjects with BSA $\geq 1.6 \text{ m}^2$: Mean aortic gradient ≥ 20 and ≤ 40 mmHg, EOA ≥ 0.8 and $\leq 1.1 \text{ cm}^2$ AND/OR DVI ≥ 0.25 and ≤ 0.35
 
For subjects with BSA $< 1.6 \text{ m}^2$: Mean aortic gradient ≥ 20 and ≤ 40 mmHg, EOA $\geq 0.6 \text{ cm}^2$ and $\leq 0.9 \text{ cm}^2$ AND/OR DVI ≥ 0.25 and ≤ 0.35

Stenosis: moderate/severe	
For subjects with BSA $\geq 1.6 \text{ m}^2$: Mean aortic gradient > 40 mmHg, EOA $< 0.8 \text{ cm}^2$ AND/OR DVI < 0.25
 
For subjects with BSA $< 1.6 \text{ m}^2$: Mean aortic gradient > 40 mmHg, EOA $< 0.6 \text{ cm}^2$ AND/OR DVI < 0.25

Paravalvular regurgitation: moderate	Moderate paravalvular regurgitation (per echo criteria in CIP)
Paravalvular regurgitation: severe	Severe paravalvular regurgitation (per echo criteria in CIP)
Transvalvular regurgitation: moderate	Moderate paravalvular regurgitation (per echo criteria in CIP)
Transvalvular regurgitation: severe	Moderate or severe transvalvular regurgitation (per echo criteria in CIP)

Notes:

1. DVI = Doppler Velocity Index (LVOT VTI/valve VTI)
2. For subjects LVOT diameter > 2.5 cm, the DVI criteria for significant (moderate or severe) stenosis is 0.2
3. Reporting of prosthetic valve dysfunction will be based on core lab values (if available).
4. Prosthetic valve dysfunction events are not reported as adverse events, unless the dysfunction is accompanied with clinical sequelae at the time of event detection, and the clinical sequelae are chronologically and physiologically associated with the dysfunction. However, prosthetic dysfunctions that are associated with adverse events, and that meet the definition of a serious adverse event, should be reported as such.

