APPENDIX G. EVENT CODE LIST

Myocardial Infarction

- 100 Peri-procedural myocardial infarction
- 101 Spontaneous myocardial infarction

Stroke and TIA

- 102 Disabling stroke: ischemic
- 103 Disabling stroke: hemorrhagic
- 104 Disabling stroke: undetermined origin
- 105 Non-disabling stroke: ischemic
- 106 Non-disabling stroke: hemorrhagic
- 107 Non-disabling stroke: undetermined origin
- 108 Transient ischemic attack

Bleeding Complications

- 110 Life threatening or disabling bleeding event
- 111 Major bleeding event
- 112 Minor bleeding event

Acute Kidney Injury

- 113 Acute kidney injury: stage 1
- 114 Acute kidney injury: stage 2
- 115 Acute kidney injury: stage 3

Vascular Access and Access Site Complications

Major

- 120 Major vascular complication: aortic dissection, aortic rupture, LV perforation, or new apical aneurysm/pseudoaneurysm
- 121 Major vascular complication: access site or access site-related vascular injury (dissection, stenosis, perforation, etc)
- 122 Major vascular complication: distal embolization from vascular source
- 123 Unplanned endovascular or surgical intervention
- 124 New ipsilateral lower extremity ischemia
- 125 Surgery for access site-related nerve injury
- 126 Permanent access site-related nerve injury
- 127 Other major vascular complication

Minor

- 130 Minor vascular complication: access site or access site-related vascular injury
- 131 Minor vascular complication: distal embolization from vascular source
- 132 Unplanned endovascular stenting or unplanned surgical intervention not meeting criteria for major complication
- 133 Vascular repair or need for vascular repair
- 134 Other minor vascular access site complication
- 140 Failure of closure device leading to alternative treatment

Other TAVI-Related Complications

- 150 Conversion to open surgery
- 151 Unplanned use of CPB
- 152 Coronary artery obstruction
- 153 Ventricular septal perforation
- 154 Mitral valve apparatus damage or dysfunction
- 155 Cardiac tamponade
- 156 Prosthetic valve thrombosis
- 157 Valve migration
- 158 Valve embolization
- 159 Ectopic valve deployment
- 160 TAV in TAV deployment
- 161 Major hemolysis
- 162 Minor hemolysis
- 163 Prosthetic valve endocarditis: definite
- 164 Prosthetic valve endocarditis: possible
- 165 Major frame fracture
- 166 Minor frame fracture
- 167 Other TAVI-related complication

Conduction Disturbances and Arrhythmias

- 170 Atrio-ventricular block, 1°
- 171 Atrio-ventricular block, 2°

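### The definite and possible rules for prosthetic valve endocarditis overlap, so one event can validly be coded 163 or 164

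*Protocol*

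**What the plan says.** The prosthetic valve endocarditis box in Protocol Appendix E.2 gives several alternative routes to a definite case. Apart from histologic or microbiologic proof, they rest on counts of major and minor criteria: "2 major criteria, or" then "1 major criteria or 3 minor criteria", and finally "5 minor criteria".

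After listing the criteria, the same box sets a second rule, for the lower grade (possible): "If only 1 major and 1-2 minor criteria are fulfilled, or if only 3-4 minor criteria are fulfilled, the event will be coded as" that lower grade.

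Appendix G gives the two outcomes separate codes: "163 Prosthetic valve endocarditis: definite" and "164 Prosthetic valve endocarditis: possible". The opening of Appendix E makes the text binding on coders: "Site investigators and the CEC will code events according to these definitions". Protocol section 5.7.2 (Table 7) lists prosthetic valve endocarditis, as a single undivided item, among the VARC-2 events that must be reported whether serious or not. The SAP neither defines nor analyses endocarditis.

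**The concern.** A case definition with two certainty grades works only if an event falls into one grade. Here the word joining the major and minor counts in the disputed line makes a single major criterion, or any three minor criteria, enough for definite. The later rule sends most of those same findings to possible. Two coders with identical records could assign different codes, and each could point to the protocol.

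At stake is the split between codes 163 and 164 for a reportable valve complication. The study is meant to document safety at up to 60 sites, over three and possibly five years of follow-up. The CEC's minimum remit (Protocol section 5.7.7) covers deaths and events that count toward safety endpoints. Endocarditis coding may therefore rest on the sites alone, which makes a clear written rule more important.

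**Working it through.** The documents state no figure to reproduce, so the check is a logical enumeration of the rules.

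**Inputs (Protocol Appendix E.2).** There are two major headings (blood cultures; endocardial involvement) and six minor criteria (predisposition, fever, vascular, immunological, microbiological, echocardiographic). Let M be the number of major criteria met (0 to 2) and m the number of minor criteria met (0 to 6). That gives 3 × 7 = 21 count combinations, or 2^8 = 256 individual patterns. The routes that do not depend on these counts (histology or microbiology, findings at re-operation, findings at autopsy) are left out.

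**Rules.**
- Definite as written: M ≥ 2, or M ≥ 1, or m ≥ 3, or m ≥ 5.
- Definite if the disputed line joins its parts: M ≥ 2, or (M ≥ 1 and m ≥ 3), or m ≥ 5.
- Possible: (M = 1 and m = 1 or 2), or (M = 0 and m = 3 or 4).

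**Results.**

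| | Definite as written | Definite with the parts joined |
|---|---|---|
| Combinations that are definite | 18 of 21 | 13 of 21 |
| Combinations that are possible | 4 | 4 |
| Combinations that are both | 4 | 0 |
| Patterns that are definite | 234 of 256 | 155 of 256 |
| Patterns that are both | 77 of 77 possible | 0 of 77 possible |

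The 18 follows because only M = 0 with m = 0, 1 or 2 escapes the written rule (21 − 3). The 13 is 7 (M = 2) + 4 (M = 1, m = 3 to 6) + 2 (M = 0, m = 5 or 6). The 77 is 2 × (6 + 15) for one major with 1 or 2 minor, plus 20 + 15 for 3 or 4 minor alone.

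**Redundancy.** Any case with M ≥ 2 already has M ≥ 1, and any case with m ≥ 5 already has m ≥ 3. As written, the two-major and five-minor lines therefore add no case. With the parts joined, both lines do work.

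**Which combinations are over-called, relative to the joined rule.**
- If the definite line is applied literally, 18 − 13 = 5: the four shared combinations plus M = 1, m = 0.
- If the possible rule overrides, the four shared ones go to code 164 and one remains: M = 1, m = 0. The ordering is then inverted, because one major criterion alone is definite while one major with 1 or 2 minor is only possible.

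These are counts of rule combinations, not of patients. Combinations are not equally likely, so none of these figures is an error rate.

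**The case against.** The strongest reply is that the possible rule is the more specific of the two and is phrased as mandatory. A coder who reads the whole box could let it govern and send all four shared combinations to 164. Only one major with no minor would then be over-called. That cell may be nearly empty, since a predisposing heart condition is itself a minor criterion. If an implanted prosthesis counts as one, every implanted subject starts with one minor criterion. This reply stands in part: it is a reasonable reading, and certain overcounting is not shown. But no text sets that precedence, the documents do not say whether the prosthesis counts as a predisposition, and the inversion remains.

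A reader might infer more than the documents support, in three ways.
- That the definite endocarditis rate is inflated by some factor. The plan specifies no such rate, gives no expected incidence, and does not fix which rule coders follow.
- That a planned result is affected. Endocarditis is not in the primary endpoint, device success, the hemodynamic measures, the early safety composite or the pacemaker endpoint. The SAP's code list for the composite (section 3.7.3.4) includes neither 163 nor 164. Table 7 does not split the item, so moving an event between the codes changes neither its reporting nor the combined count of 163 and 164.
- That the CEC will resolve every case. Appendix E names the CEC as a coder, but endocarditis sits in E.2 with other complications, not among the E.1 safety endpoint definitions. Section 5.7.7 makes review beyond the minimum depend on a sponsor request.

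**Conclusion.** The point holds as a contradiction within an operative coding rule. All four combinations in the possible rule also meet the definite rule, so an event with any of them can validly be coded 163 or 164. Definite cases can be overcounted, in five combinations on the literal reading or in one if the possible rule overrides.

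The effect is confined to the reported 163/164 split. The hypothesis test, the sample size, the early safety composite and every SAP analysis are unaffected. The number of events cannot be computed from the documents and is likely to be small.

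The conclusion rests on the current protocol text alone. Two things are taken as given: the two major headings count as one criterion each, and each count in the definite list means at least that many. The CEC charter was not available, so whether it already settles the matter is unknown.

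**What to change.** Reconcile the two rules in Appendix E.2 so that definite and possible exclude each other. Reading the disputed line as 1 major and 3 minor criteria does this: the overlap falls from four combinations to none, and the two-major and five-minor lines regain a function. One major with no minor would then meet neither count-based rule, and the sponsor should confirm that this is intended.

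Issue the correction to sites and the CEC, and check that the CEC charter agrees. Recheck the coding of any event given 163 on that line alone, by the CEC where it adjudicates such events and otherwise by the site with the sponsor.

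The cost is one changed word in a coding definition, a notice to sites and the CEC, and a recheck that probably involves few events. No treatment, visit, endpoint or SAP analysis changes.
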